10. STUDY ACTIVITIES

[Table 2](#) provides a tabular summary of all scheduled visits and procedures to be performed during the clinical study.

All ophthalmic assessments will be performed *bilaterally*.

10.1. Day 1 (Visit 1): Screening/Baseline/Randomization/First Dose

Subjects will provide written informed consent before any study-related screening procedures are conducted. For minor subjects, signed informed consent will be obtained from the subject's parent or legal guardian, and assent will be obtained from the subject following IRB guidelines.

Subjects will undergo screening/baseline evaluations to determine eligibility for the study. Following review of inclusion/exclusion criteria, the site will access the IWRS to randomize the subject to study treatment and assign the study medication kit to be dispensed. Subjects (or caregivers, if the subject is not able to self-administer the medication) will receive instruction on administration procedures and administer the first dose. Adverse events will be assessed post dose, and study material accountability will be performed.

Day 1 procedures include the following:

- Informed consent/assent
- Demographics
- Medical and ocular histories
- Urine pregnancy test (females of childbearing potential only)
- Prior and concomitant medications/therapies
- BP/HR
- MRD (from external photograph)
- Pupil diameter measurement (from external photograph)
- Snellen visual acuity
- SLE
- CFS
- IOP
- Dilated ophthalmoscopy/fundus exam
- Review inclusion/exclusion criteria
- Randomization of eligible subjects via IWRS (see Section 8.2)
- Dispense study medication Box 1 per IWRS assignment
- Instruct the subject on use and storage of study medication (see Section 8.6.2)
- The subject (or caregiver, if the subject is not able to self-administer the medication) will administer allocated study medication, 1 full drop in each eye (if a full drop is

not instilled into the eye, the subject will wait approximately 10-15 seconds and administer a second drop). After a full drop is instilled in each eye, the subject should keep the eyes gently closed for approximately 30 seconds.

- AE assessment
- Study medication accountability

10.2. Days 2 through 14

From Days 2 through 14, randomized study medication will be administered in each eye QD in the morning and subjects will return to the clinical site on Day 14 ± 3 days in the morning after instillation of study medication at home. Note: Contact lenses must be removed prior to instillation of study medication and must not be reinserted for at least 15 minutes after study medication instillation. Contact lenses must not be worn during study visits.

10.3. Safety Follow-up Visits

10.3.1. Day 14 ± 3 (Visit 2)

On Day 14 ± 3 (Visit 2), subjects will return all opened and unopened study medication materials and undergo safety assessments. Site personnel will dispense study medication (Box 2) and conduct study medication accountability procedures.

Day 14 procedures include the following:

- Collect Box 1, containing all opened and unopened study medication materials (unit-dose vials and pouches), from the subject
- Concomitant medication review
- AE assessment
- BP/HR
- Pupil diameter measurement (from external photograph)
- Snellen VA
- SLE
- CFS
- Dispense study medication Box 2
- Study medication accountability

10.3.2. Days 15 through 42

From Days 15 through 42, randomized study medication will be administered in each eye QD in the morning and subjects will return to the clinical site on Day 42 ± 3 days in the morning after instillation of study medication at home. Note: Contact lenses must be removed prior to instillation of study medication and must not be reinserted for at least 15 minutes after study medication instillation. Contact lenses must not be worn during study visits.

10.3.3. Day 42 ± 3 (Visit 3)

On Day 42 ± 3 (Visit 3), subjects will return all opened and unopened study medication materials and undergo safety assessments. Site personnel will dispense study medication (Box 3) and conduct study medication accountability procedures.

Day 42 procedures include the following:

- Collect Box 2, containing all opened and unopened study medication materials (unit-dose vials and pouches), from the subject
- Concomitant medication review
- AE assessment
- BP/HR
- Pupil diameter measurement (from external photograph)
- Snellen VA
- SLE
- CFS
- IOP
- Dispense study medication Box 3
- Study medication accountability

10.3.4. Days 43 through Day 84

From Day 43 through the morning of Day 84, randomized study medication will be administered in each eye QD in the morning and subjects will return to the clinical site on Day 84 ± 3 days in the morning after instillation of study medication at home. Note: Contact lenses must be removed prior to instillation of study medication and must not be reinserted for at least 15 minutes after study medication instillation. Contact lenses must not be worn during study visits.

10.3.5. Day 84 ± 3 (Visit 4): Final Treatment Visit

On Day 84 ± 3 , subjects will return all opened and unopened study medication materials and participate in final safety and tolerability assessments. Site personnel will conduct final study medication accountability procedures.

Visit 4 procedures include the following:

- Collect Box 3, containing all opened and unopened study medication materials (unit-dose vials and pouches), from the subject
- Urine pregnancy test (females of childbearing potential only)
- Concomitant medication review
- AE assessment
- Study medication tolerability assessment
- BP/HR
- Pupil diameter measurement (from external photograph)
- Snellen VA
- SLE
- CFS
- IOP
- Dilated ophthalmoscopy/fundus exam
- Final study medication accountability

10.4. Early Discontinuation Assessment Procedures

If a study subject is discontinued from study medication before Day 84 (Visit 4) and after Day 1 (Visit 1), procedures performed will include the following:

- Collect all opened and unopened study medication materials (opened and unopened unit-dose vials and pouches) from the subject
- Urine pregnancy test (for females of childbearing potential only)
- Concomitant medication review
- AE assessment
- Study medication tolerability assessment (rating by subject)
- BP/HR (taken after 3 minutes at rest)
- Pupil diameter measurement (from external photograph)
- Snellen VA
- SLE
- CFS
- IOP
- Dilated ophthalmoscopy/fundus exam
- Study medication accountability

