8.2.1. Unmasking During the Study Period

Should it be necessary to unmask a subject's treatment assignment in case of emergency, the Investigator may obtain the treatment code for a given randomized subject from the IWRS. The treatment code is to be obtained only if a medical emergency exists and knowledge of the medication being taken will influence the medical management of the subject.

The following procedure should be followed:

1. The Investigator should contact the Medical Monitor via phone immediately before unmasking a subject unless it is not possible to do so without risk to the subject.
2. The Investigator should document the AE and justification for unmasking in the Study Summary and Comments pages of the eCRF.
3. If the subject is to be discontinued from study medication, then ALL procedures described in the Early Discontinuation Visit ([Section 10.4](#)) should be completed.
4. The Investigator should contact Oculos at [contact] within 24 hours with the subject number and details of the AE or SAE and any action taken.

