8.5. Discontinuation of Study Medication

If a subject becomes pregnant during the study, the subject will be withdrawn from study medication and followed through the conclusion of the pregnancy ([Section 9.6](#)).

Subjects may be discontinued from study medication because of either of the following:

- Adverse event: A clinically significant or serious AE that in the Investigator's or Medical Monitor's judgment, suggests that continued administration of study medication is not in the subject's best interests for safety reasons. Additionally, if an AE requires treatment, the Investigator in consultation with the Medical Monitor may determine that study medication should not be concurrently administered with a required concomitant medication.
- Subject request: Subject requests to be withdrawn from study medication.

When possible, a decision to discontinue a subject from study medication should first be discussed with the Medical Monitor. If a subject is discontinued from study medication, every effort should be made to encourage the subject to continue to attend study visits to be followed for safety, rather than withdrawing the subject from the study or, failing that, to perform all early discontinuation assessment procedures at the visit the subject is withdrawn ([Section 10.4](#)). Reasons for considering subject withdrawal from the study are discussed in [Section 7.3](#).

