6.2 Handling of Early Termination Visit Information

If a patient is terminated early from this study the early termination visit data will be analyzed at the closest scheduled visit. If the closest visit has valid data, the early termination data will be assigned to the next available visit.

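### The protocol gives two different triggers for the Early Discontinuation assessments, and the SAP does not say how to handle subjects who stop drug but stay in follow-up

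*Protocol*

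**What the plan says.** Three protocol sections and one SAP section bear on the point.

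- **Protocol 10.4** sets the general rule: "If a study subject is discontinued from study medication before Day 84" and after Day 1, the listed assessments are due, and they include tolerability, IOP and the dilated fundus exam. It makes no exception for a subject who stays in the study.
- **Protocol 8.2.1** uses the same trigger: "If the subject is to be discontinued from study medication, then ALL procedures described in the Early Discontinuation Visit" should be completed. Its scope is narrow, because it belongs to the emergency unmasking procedure: "The treatment code is to be obtained only if a medical emergency exists".
- **Protocol 8.5** puts retention first. When a subject stops drug, "every effort should be made to encourage the subject to continue to attend study visits to be followed for safety". The discontinuation assessments are the fallback: "failing that, to perform all early discontinuation assessment procedures at the visit the subject is withdrawn".
- **SAP 6.2** is written for leaving the study: "If a patient is terminated early from this study the early termination visit data will be analyzed at the closest scheduled visit". It adds: "If the closest visit has valid data, the early termination data will be assigned to the next available visit".

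The Early Discontinuation column in Protocol Table 2 and SAP 12 does not say whether it means stopping medication or leaving the study. SAP 8.7 tabulates tolerability only at Day 84.

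**The concern.** Stopping drug and leaving the study are separate events in this plan. SAP 7.2 summarises them separately, and SAP 8.9 counts separately the subjects who left the study and those who stopped treatment because of an adverse event. Protocol 8.5 encourages sites to create a group that is off drug but still attending. For that group 10.4 requires the discontinuation assessments, 8.5 does not ask for them, and the SAP does not say where the results would go.

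Safety is the only objective, and tolerability, tonometry and fundus findings are named endpoints (Protocol 11.5). Subjects who stop because the drops trouble them are informative for exactly these measures. If sites read the sections differently, some of these subjects will be assessed soon after their last dose and others weeks later. The by-visit tables would not show the difference, because the SAP defines no marker for off-treatment results.

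**Working it through.** The plan states no figure that could be reproduced: there is no sample-size calculation, no dropout rate and no test. The check sets the schedule beside the competing triggers.

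**Step 1. Which assessments depend on the trigger?** Post-baseline time points in Protocol Table 2:

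| Assessment | Day 14 | Day 42 | Day 84 | Early Discontinuation |
|---|---|---|---|---|
| Tolerability | no | no | yes | yes |
| Dilated fundus exam | no | no | yes | yes |
| IOP | no | yes | yes | yes |
| Pupil diameter, VA, slit lamp, staining, BP/HR | yes | yes | yes | yes |
| Adverse events | yes | yes | yes | yes |

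The first three rows are the sensitive ones. For the fourth row only the timing of one extra measurement is in question.

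**Step 2. Delay for a subject who stops on Day d and stays, following 8.5 alone.**

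- Tolerability and fundus: 84 − d days after the stop.
- IOP: 42 − d days if d is before Day 42, otherwise 84 − d.

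For d = 20 (an illustration):

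- Tolerability and fundus: 84 − 20 = 64 days (61 to 67 with the ±3-day window).
- IOP: 42 − 20 = 22 days (19 to 25 with the window).

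For d = 70 all three come 84 − 70 = 14 days after the stop. The delay shrinks as the stop moves later.

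Under 10.4 the three assessments would be made at a discontinuation visit. No section links that visit to the last dose by a window, so its delay is expected to be short but is not fixed.

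**Step 3. What if SAP 6.2 were applied to a Day 20 discontinuation visit?** The distances are 20 − 14 = 6 days to Day 14 and 42 − 20 = 22 days to Day 42, so Day 14 is closest.

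- Read visit by visit: Day 14 normally holds valid data, so the record moves to Day 42. A retained subject also attends Day 42, and two records then compete for one slot.
- Read assessment by assessment: Day 14 holds no tolerability, fundus or IOP result, so these three land on Day 14. The tolerability rating then falls outside SAP 8.7, which tabulates only Day 84.

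On either reading the early tolerability rating does not reach the Day 84 table.

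**Step 4. How many subjects?** The documents give no rate of early stopping. Assume 5% to 15%:

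- RVL-1201: 0.05 × 150 = 7.5 and 0.15 × 150 = 22.5, about 8 to 23.
- Vehicle: 0.05 × 75 = 3.75 and 0.15 × 75 = 11.25, about 4 to 11.

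These are ceilings. A subject who stops drug and also leaves is due the assessments under both 10.4 and 8.5. Only those who stop and stay are caught between the two.

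**The case against.** The strongest reply is that this is an ambiguity, not a strict contradiction. Protocol 8.5 is mainly a retention instruction. It refers to 10.4 and does not forbid the assessments in a subject who stays, so a site that always follows 10.4 breaches nothing. That is fair, but a site that follows 8.5 as written will not do the assessments in a retained subject. The data still differ by reading, and no section settles it.

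Much of the safety information is also secure. Adverse events are sought at every visit and recorded to Day 84. Those leading to discontinuation of study medication are listed and tabulated (SAP 8.9). All collected data appear in listings (SAP 7.1), so an extra discontinuation record would not be lost. This stands, and it confines the problem to tolerability, fundus and IOP and to where they appear in the tables.

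A result obtained at Day 84 off drug is a genuine Day 84 observation, and reporting it as such is not an error in itself. This also stands. The difficulty is that it cannot be told apart in the tables from a Day 84 result on treatment.

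A reader might infer three stronger things that the documents do not support:

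- **That on-drug safety data in general hang on the choice of section.** Visits before the stop are identical under both readings.
- **That 8.2.1 is a second general rule.** It governs emergency unmasking only, so 10.4 alone carries the general trigger.
- **That 10.4 guarantees results on the day of the stop.** No window ties the discontinuation visit to the last dose.

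**Conclusion.** The point holds for subjects who stop study medication but remain in follow-up. Protocol 10.4 and 8.5 give different triggers for the same assessments, SAP 6.2 covers neither trigger for this group, and nothing in the documents reconciles them. Whether tolerability, fundus and IOP are assessed near the end of exposure therefore depends on the section a site follows.

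The size is modest and uncertain. In the Day 20 example the delay under 8.5 is about 22 days for IOP and 64 days for tolerability and fundus; later stops give shorter delays. It would be tempting to say that 8-23 active subjects are affected. The documents do not support that: the figure rests on an assumed 5-15% rate and would be reached only if every early stopper stayed. The same limit applies to the 4-11 Vehicle subjects.

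The study is descriptive with no tests, so no error rate or power is at stake. What is at stake is the completeness and interpretability of three safety measures in a small, informative group. It should be corrected, but it does not undermine the trial.

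**What to change.** 1. **Protocol 8.2.1, 8.5 and 10.4:** reconcile them to one stated trigger for the Early Discontinuation assessments, and label the matching column in Table 2 and SAP 12 accordingly. Which trigger applies is for the sponsor to decide; this review does not choose.
2. **SAP 6.2:** extend it to subjects who stop drug but stay. Any assessment taken at drug stop should be kept as its own record, so that it neither replaces nor competes with a scheduled visit the subject attends.
3. **SAP 8.7:** tabulate tolerability ratings from the Early Discontinuation visit alongside the Day 84 ratings. Changing SAP 6.2 alone would still leave these ratings out of the table.

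The cost is wording changes in the two documents and one extra summary row. Every assessment is already in Table 2, so no procedure is added.

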11. STATISTICS

11.1. General Considerations

This is a Phase 3 study to evaluate the safety of QD treatment with RVL-1201 Ophthalmic Solution (oxymetazoline hydrochloride ophthalmic solution, 0.1%) compared to Vehicle (placebo) for the treatment of acquired ptosis over an extended dosing period of 12 weeks.

Subjects will be randomized in a 2:1 ratio of RVL-1201 Ophthalmic Solution to Vehicle into 2 treatment groups and treated for 84 days:

- RVL-1201 Ophthalmic Solution 1 drop in each eye QD in the morning (N = 150)
- Vehicle (placebo) 1 drop in each eye QD in the morning (N = 75).

A biostatistician will perform statistical analyses as agreed with the Sponsor according to the Statistical Analysis Plan (SAP).

A detailed SAP will be finalized prior to database lock. Descriptive statistics (n, mean, median, standard deviation [SD], minimum, and maximum for continuous data; frequencies and percentages for categorical data) will be used to summarize study data. No statistical tests will be performed for any of the assessments.

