11.5. Safety Endpoints

The safety of RVL-1201 compared to Vehicle will be evaluated by the following endpoints:

1. Comparison of ocular and non-ocular AEs by:
 - a. Frequency
 - b. Intensity
 - c. Relationship to treatment
 - d. Serious adverse events
 - e. Adverse events leading to withdrawal of study medication
2. Comparison of subjects with findings on the following measures:
 - a. Slit-lamp examination
 - b. Corneal fluorescein staining
 - c. Pupil diameter
 - d. Dilated ophthalmoscopy/fundus examination
 - e. Tonometry
 - f. Snellen VA (corrected)
 - g. Vital signs (BP/HR)
3. Comparison of tolerability as measured by the tolerability scale.

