11.6. Safety Analyses

The safety of RVL-1201 will be compared to Vehicle with analysis of safety variables including bilateral ophthalmic examinations (Snellen VA, SLE/CFS, measurement of pupil diameter from external photographs, dilated ophthalmoscopy/fundus examination, and tonometry), vital signs (BP/HR), and AEs. The ocular tolerability of study medication will be rated by the subject. Safety data will be presented in tables of descriptive statistics and frequency distribution. All summary tables will be supported with individual subject data listings.

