7. STATISTICAL ANALYSIS

7.1 General Considerations

This is a Phase 3 study to evaluate the safety of daily treatment with RVL-1201 Ophthalmic Solution (oxymetazoline hydrochloride ophthalmic solution, 0.1%) compared to Vehicle (placebo) for the treatment of acquired ptosis over an extended dosing period of 12 weeks.

Subjects will be randomized in a 2:1 ratio of RVL-1201 Ophthalmic Solution to Vehicle into 2 treatment groups and treated for 84 days:

- RVL-1201 Ophthalmic Solution 1 drop in each eye QD in the morning (N = 150)
- Vehicle (placebo) 1 drop in each eye QD in the morning (N = 75)

Descriptive statistics will be used to summarize continuous outcomes (number of subjects [N], mean, standard deviation or standard error of the mean, median, maximum, and minimum) and categorical variables (frequency and percentage) at each assessment time point.

All data collected in the study database will be presented in the listings.

All statistical analyses and reporting will be performed using the SAS® System Version 9.4 or later.

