8. SAFETY MEASURES

Safety data will be presented in tables of descriptive statistics and frequency distribution using the safety population. All summary tables will be supported with individual subject data listings.

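### The safety endpoints are worded as comparisons with Vehicle, but the plan summarises each arm separately and gives no between-arm difference or interval

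*Protocol*

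**What the plan says.** Protocol 11.5 introduces the endpoints with "The safety of RVL-1201 compared to Vehicle will be evaluated by the following endpoints". Its three groups are all worded as comparisons: adverse events ("Comparison of ocular and non-ocular AEs by" frequency, intensity, relationship, seriousness and withdrawal of medication), examination and vital-sign results ("Comparison of subjects with findings on the following measures"), and the tolerability scale. Protocol 11.6 repeats the framing: "The safety of RVL-1201 will be compared to Vehicle with analysis of safety variables".

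The planned statistics are all within-arm. Protocol 11.1 lists n, mean, median, SD, range, frequencies and percentages, and adds "No statistical tests will be performed for any of the assessments". SAP 7.1 says "Descriptive statistics will be used to summarize continuous outcomes" and lists the same kinds of quantity, with SD or standard error of the mean. SAP 8 says "Safety data will be presented in tables of descriptive statistics and frequency distribution using the safety population". SAP 8.1 to 8.8 tabulate results by treatment group, with change from baseline for the continuous measures, and SAP 8.9 gives numbers and percentages of subjects by group.

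Neither document plans a risk difference, mean difference, ratio or between-arm confidence interval, and neither says how the comparison will be judged. Protocol 11.2 and SAP 4 say that the sample size does not come from a statistical calculation.

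**The concern.** The quantity that the endpoints name is a contrast between randomised arms, yet the tables estimate only each arm on its own. A vehicle-controlled safety study is asked how much more often an event occurs on drug than on vehicle, and how large an excess the data leave open. Two percentages side by side answer the first part only roughly and the second not at all.

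The Vehicle arm has 75 subjects, so its percentages are imprecise. That imprecision passes straight into the contrast, and no planned column shows it. If intervals are added only after unmasking, the choice of events to receive one is open to selection.

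**Working it through.** **Inputs from the documents.** 150 subjects on RVL-1201 and 75 on Vehicle (Protocol 6.2 and 11.1). These agree with the total of about 225 and the 2:1 ratio: 150 + 75 = 225, 150/75 = 2. There is no sample size calculation to reproduce. No event rate, margin, alpha or power is stated.

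**Assumptions.** Every event rate below is assumed. Intervals are two-sided 95%, z = 1.96, with the full planned denominators.

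**1. Interval for a risk difference (Newcombe).** For each arm with proportion p and size n, the Wilson limits (l, u) are

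[p + z²/(2n) ± z·√(p(1−p)/n + z²/(4n²))] / (1 + z²/n).

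With d = p1 − p2 (RVL-1201 minus Vehicle):

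- lower limit = d − √[(p1 − l1)² + (u2 − p2)²]
- upper limit = d + √[(u1 − p1)² + (p2 − l2)²]

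Worked case, 4% in each arm (6/150 and 3/75), in percentage points. The Wilson limits are 1.85 to 8.45 for RVL-1201 and 1.37 to 11.11 for Vehicle.

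- upper = √[(8.45 − 4)² + (4 − 1.37)²] = √(19.8 + 6.9) = 5.2
- lower = −√[(4 − 1.85)² + (11.11 − 4)²] = −√(4.6 + 50.6) = −7.4

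| Assumed counts, RVL-1201 vs Vehicle | Difference (points) | 95% interval (points) |
|---|---|---|
| 0/150 vs 0/75 | 0 | −4.9 to +2.5 |
| 6/150 vs 3/75 (4% each) | 0 | −7.4 to +5.2 |
| 12/150 vs 6/75 (8% each) | 0 | −9.0 to +6.9 |
| 30/150 vs 15/75 (20% each) | 0 | −11.8 to +10.3 |
| 15/150 vs 4/75 (10% vs 5.3%) | +4.7 | −3.8 to +11.3 |

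The zero-event row is a between-arm result. The familiar one-sided 95% bound for no events in 150 subjects, 1 − 0.05^(1/150) = 2.0%, describes one arm only and does not answer the comparison.

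**2. How often the observed rates would mislead.** Suppose RVL-1201 truly doubles the Vehicle rate. Summing the exact binomial probabilities over all outcomes in which the observed RVL-1201 rate is equal to or below the Vehicle rate gives 22% of trials at 2% vs 4%, 9% at 5% vs 10%, and 2% at 10% vs 20%.

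**3. Continuous measures.** For an unadjusted difference in means with a common SD, the 95% half-width is 1.96 × √(1/150 + 1/75) = 1.96 × 0.1414 = 0.28 SD.

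The Safety population also requires a post-dose visit (Protocol 11.3.1, SAP 5), so actual denominators may be smaller and the intervals wider.

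**The case against.** The strongest reply is that this is a declared descriptive study. It has no tests, no efficacy analysis, no margin, no decision rule, and a size set by regulatory need for safety data. Randomised arms shown side by side are a form of comparison, so no commitment is broken. That stands, and it is why this is not an error.

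It is also true that a reader could derive unadjusted intervals from the reported n, percentages, means and SDs. The point is therefore about presentation and pre-specification; the information is not lost. What the arm summaries do not supply is a baseline-adjusted difference, or a list of events fixed before unmasking.

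Some stronger readings are tempting:

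- A reader might infer that the sponsor will conclude that the arms do not differ. Neither document says so; that is only a risk of interpretation.
- A reader might infer that Protocol 11.1 rules out intervals. It excludes tests only, and an interval without a p-value is compatible with it. The gap lies in the lists of planned statistics.
- A reader might infer that the missing intervals contradict Protocol 11.5. They do not, because the protocol never says what form the comparison takes.

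The last objection is that many unadjusted intervals would bring informal testing back. Intervals for every eye and post-baseline visit would number 4 for IOP, 6 for pupil diameter and 9 for systolic BP, diastolic BP and heart rate, 19 in all. This stands, and it is a reason to keep the list short.

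**Conclusion.** The gap is real and modest. The endpoints are contrasts with Vehicle, and the plan specifies no estimate of a contrast and no measure of its uncertainty. At 150 and 75 subjects, equal observed rates remain compatible with an excess on RVL-1201 of about 2.5 points when no events occur and about 10 points when the rate is 20% in each arm. These sizes rest on assumed rates, two-sided 95% Newcombe intervals and full planned denominators; the documents give no rates of their own. The documents do not support a finding that the plan is wrong, contradictory or committed to a claim of no difference. A short pre-specified set of intervals is worth adding because it lets the report state what excess the trial can and cannot exclude.

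**What to change.** Before database lock, add to SAP 8.9 the RVL-1201 minus Vehicle risk difference with a 95% Newcombe interval, counted by subject, for:

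1. any TEAE;
2. any TEAE with a suspected relationship to study medication;
3. any TEAE leading to discontinuation of study medication;
4. any TESAE;
5. any ocular TEAE, identified from the OD/OS recording in the eCRF.

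The first four come from the overall summary already planned in SAP 8.9. The fifth needs a subject-level flag and one new row.

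Optionally, add to SAP 8.1, 8.3 and 8.8 the Day 84 difference in mean change from baseline with a 95% confidence interval, from an ANCOVA with baseline value and treatment as terms. Do this for IOP and pupil diameter, separately for OD and OS, and for systolic BP, diastolic BP and heart rate. That is 2 + 2 + 3 = 7 intervals and one model that the SAP does not now contain.

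Report no p-values. State that the intervals are descriptive and not adjusted for multiplicity.

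The cost is a column and a row in an existing table, plus a small amount of programming if the optional part is taken. The downside is chance exclusion of zero: at a nominal 5% each and with no true differences, about 5 × 0.05 = 0.25 intervals would be expected to exclude zero for the core list, and 12 × 0.05 = 0.6 with the optional part. Some readers may treat such an interval as a test.
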